11.4 Analysis of Pharmacokinetic and Pharmacodynamic Variables

11.4.1 *Pharmacokinetic Analyses*

The individual patient plasma concentration-time data following the first dose for Japanese intensive PK subjects will be listed and displayed graphically on linear and log scales. The plasma concentration-time data will be summarized descriptively in tabular and graphical formats (linear and log scales).

For Japanese intensive PK subjects, the plasma WVE-210201 concentration data following the first dose will be analyzed by noncompartmental PK analysis (NCA). The parameters listed in [Table 12](#) will be determined if there are sufficient data. Additional PK parameters may be evaluated if deemed appropriate. The PK parameters will be summarized by treatment group.

For sparse PK concentrations, the data will be summarized by treatment week and treatment group. All subjects will be included in the summary for the sparse time points, including intensive PK subjects.

Table 12 Pharmacokinetic Parameters

| Parameter | Definition |
|---------------------|--|
| C_{\max} | Maximum observed concentration |
| AUC_{last} | Area under the plasma concentration-time curve from time zero to the last quantifiable concentration |
| AUC_{∞} | Area under the plasma concentration-time curve from time zero to infinity |
| $T_{1/2}$ | Terminal half-life |
| CL | Total body clearance |
| V_{dss} | Volume of distribution at steady state |

11.4.2 Immunogenicity

Immunogenicity analyses will be performed for all patients. Summary statistics will be provided as appropriate.

11.4.3 Muscle tissue concentration of WVE-210201

If performed, for all subjects, the tissue concentration of WVE-210201 will be summarized by treatment group.

11.5 Interim Analyses

Multiple interim efficacy analyses are planned for the Double-blind Treatment Period in this Phase 2/3 study and will include analysis of dystrophin and NSAA data.

The interim analyses will be performed by an independent statistical center (ISC) and the results will be reviewed by the DMC. Sponsor personnel responsible for the conduct of this trial will not be unblinded at the time of the interim analyses and will not have access to the interim analysis results. Procedures pertaining to the ISC and its communication with the DMC are described in an ISC Charter and Data Access Plan.

11.5.1 Dystrophin Interim Analyses

Interim analyses of dystrophin will determine if efficacy is demonstrated prior to study conclusion and may allow for stopping randomization to the WVE-210201 3 mg/kg arm. The

first interim dystrophin analysis will compare dystrophin protein levels between WVE-210201 and placebo using the Week 12 open biopsies collected from up to the first 30 patients randomized. The second interim dystrophin analysis will compare dystrophin protein levels between WVE-210201 and placebo from approximately 40 patients with Week 22 open biopsies (collected from the 31st through 70th patient). The dystrophin interim analyses will be supplemented with dystrophin data from the ongoing OL extension study to the Phase 1 trial (WVE-DMDX51-002). A final analysis of dystrophin will occur when up to 80 patients (collected from the 71st through a maximum of the 150th patient) have Week 46 open biopsies. The significance thresholds for the dystrophin analyses are described in [Section 11.3.2.1](#). If the first or second interim dystrophin analysis results in a significant WVE-210201 treatment effect, randomized patients will continue to complete 48 weeks of follow-up to assess clinical outcomes and other endpoints.

Randomization to the WVE-210201 3 mg/kg treatment arm may be stopped based on the interim analysis of dystrophin. Specifically, randomization to the WVE-210201 3 mg/kg treatment arm will stop, if there is a high posterior probability that the high dose is effective, and the low dose is less efficacious of the high dose. The specific thresholds are included in the SAP.

If randomization to the 3 mg/kg treatment arm is stopped, patients originally randomized to the 3 mg/kg treatment arm will be transitioned to the WVE-210201 4.5 mg/kg treatment arm and all future patients will be randomized to WVE-210201 4.5 mg/kg or placebo at a 2:1 ratio. For clinical endpoint analyses, including the NSAA, patients originally randomized to the WVE-210201 3 mg/kg arm who transition to the WVE-210201 4.5 mg/kg treatment arm will not be included in WVE-210201 4.5 mg/kg treatment effect estimation.

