6 INVESTIGATIONAL DRUG AND PLACEBO

6.1 Method of Assigning Patients to Investigational Drug or Placebo

Treatment will be assigned through randomization performed using a centralized, interactive voice/web response system (IXRS).

6.1.1 *Double-blind Treatment Period*

Patients will be randomized in a 1:1:2:2 ratio to placebo 3 mg/kg, placebo 4.5 mg/kg, WVE-210201 3 mg/kg, and WVE-210201 4.5 mg/kg. Randomization will be stratified by age (≤ 9 years, > 9 years). Blocks of fixed size will be used within each of the randomization strata.

A separate randomization stratum will be included for the first 12 patients randomized in Japan (the Japanese PK cohort). As 4 patients are needed in each treatment arm in this cohort, these patients will be randomized in a 1:1:2:2 ratio to placebo 3 mg/kg, placebo 4.5 mg/kg, WVE-210201 3 mg/kg, and WVE-210201 4.5 mg/kg. This stratum will not include the age randomization factor. Japanese patients randomized after the Japanese PK cohort will be randomized as described above, but in strata that are separate from the non-Japanese patients.

6.1.2 *Open-label Treatment Period*

Patients randomized to WVE-210201 will continue with the dose level administered at the end of the Double-blind Treatment Period. Patients randomized to placebo will be treated with WVE-210201 at the dose level they had received at the end of the Double-blind Treatment Period. Patients and clinical site staff will remain blinded to the patient's treatment assignment from the Double-blind Treatment Period.

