11.3.2 Analyses of Efficacy Endpoints

11.3.2.1 Analysis of dystrophin protein level

A primary objective of this Phase 2/3 study is to evaluate the efficacy of WVE-210201 by assessing changes in dystrophin protein levels. Therefore, the primary efficacy endpoint for the United States and Other regions, as applicable, and the key secondary endpoint for the EU and Japan is the change in dystrophin protein level (% normal) from baseline. The treatment policy estimand, which assesses the effect of treatment initially assigned at baseline (regardless of adherence to the planned course of treatment), will be used. The analysis population will be the ITT population. The main estimator is a Bayesian analysis of covariance (ANCOVA). The model will include fixed effects for mean change from baseline in dystrophin levels at each time point for placebo and fixed effects for the increase or decrease in dystrophin compared to placebo for each treatment arm at each time point.

Let the change from baseline in dystrophin level at time point j for patient i be Y_{ij} , for $j = 1, 2, 3$ and $i = 1, \dots, n$. Time periods $j = 1, 2$, and 3 , refer to the post-baseline visits at 12, 22 and 46 weeks; each patient will have one Y_{ij} with either $j = 1, 2$, or 3 . The ANCOVA model is

$$Y_{ij} = \alpha_j + \theta_{t(i),j} + \epsilon_{ij};$$

$$\epsilon_{ij} \sim N(0, \sigma_{t(i),j}^2).$$

The $\alpha_j, j = 1, 2, 3$, parameters represent the mean change from baseline in dystrophin level at each time point for placebo-treated patients. For patient i , the treatment arm is labelled $t(i)$ with 0 for placebo, 1 for WVE-210201 3 mg/kg and 2 for WVE-210201 4.5 mg/kg. The effect of treatment T at time j is the parameter $\theta_{T,j}, T = 0, 1, 2$ and $j = 1, 2, 3$. For placebo, the effect is assumed to be 0 ($\theta_{0,j} = 0$). Thus, the treatment effect parameter for treatment T at time j represents the mean difference in the change from baseline in dystrophin at time j compared to placebo. The errors for the individual observations, ϵ_{ij} , are assumed independent and follow a normal distribution. The standard deviation, $\sigma_{T,j}, T = 0, 1, 2$ and $j = 1, 2, 3$, is specific to treatment arm and visit.

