11.3.2.2 Analysis of North Star Ambulatory Assessment (NSAA)

Another primary objective is to evaluate the efficacy of WVE-210201 by assessing changes in the NSAA. Therefore, the primary efficacy endpoint for the EU and Japan and the key secondary endpoint for the United States and Other regions is the change in NSAA from baseline over 48 weeks. The treatment policy estimand which assesses the effect of treatment initially assigned at baseline (regardless of adherence to the planned course of treatment) will be used. The analysis population will be the ITT population. The main estimator will be a Bayesian progression model (BPM) to compare the change in NSAA between patients treated with WVE-210201 and placebo treated patients^{59,60}. The placebo data from this study will be augmented with historical control data via a Bayesian meta-analytic approach.

The BPM assumes a non-parametric rate of progression of the NSAA for placebo patients and a proportional rate of slowing NSAA progression for the treated patients relative to the placebo patients at each time point. The model will include covariate effects to measure differences in the rates of progression based on patient-specific baseline covariates. Additionally, random patient variability will be accounted for using patient-level random effects of the rate of NSAA progression. Borrowing from historical control data to augment the placebo arm information will entail including a random data source effect to model the between-source variability in NSAA progression rates.

The NSAA analysis will be independent of the dystrophin analysis described in [Section 11.3.2.1](#). Let the NSAA at visit j for patient i be Y_{ij} , for $j = 0, \dots, 4$ and $i = 1, \dots, n$. The Y_{i0} observation corresponds to the baseline visit. Visits $j = 1, 2, 3, 4$ refer to the post-baseline visits (each separated by 12 weeks). Let X_i be a vector of dimension C of baseline covariates for patient i that have been standardized. The DPM is

$$Y_{ij} = \gamma_i + \exp(\theta_{t(i)} + \eta_i + \alpha X_i + \delta_{s(i)}) \sum_{k=0:j} \beta_k + \epsilon_{ij}; \\ \epsilon_{ij} \sim N(0, \sigma_{t(i),s(i)}^2).$$

Patient-specific random effects, $\gamma_i, i = 1, \dots, n$, represent the patient-specific mean NSAA at the time of randomization.

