It is assumed that $\beta_0 = 0$ and the decline in NSAA per each 12-week period for a placebo patient in this study with average baseline covariates is modelled as $\beta_k, k = 1, \dots, 4$, with the sum of all β_k equal to the total decline over 48 weeks. Each β_k is assumed to be less than or equal to zero to ensure a monotonic decline.

For patient i , the treatment arm is labelled $t(i)$ with 0 for placebo, 1 for WVE-210201 3 mg/kg and 2 for WVE-210201 4.5 mg/kg. The disease rate ratio (DRR) for treatment T is the parameter $\exp(\theta_T), T = 0, 1, 2$. For a placebo-treated patient, the DRR is assumed to be 1 ($\theta_0 = 0$). Thus, the DRR parameter for treatment T represents the multiplicative change to the mean decline of a placebo-treated patient. If the DRR is less than 1, the rate of decline for treatment T is slower than placebo; the DRR value represents the proportional slowing of NSAA progression. For example, a DRR = 0.75 corresponds to a 25% slowing in the rate of NSAA progression. The WVE-210201 treatment arms will be pooled for the NSAA analysis and the restriction that $\theta_1 = \theta_2$ incorporated into the DPM. However, if the randomization to the WVE-210201 3 mg/kg arm is stopped after an interim analysis (Section 11.5), the WVE-210201 treatment arms will not be pooled. Summaries of the posterior distribution for the DRR ($\exp(\theta_T)$) for each arm will be provided including the probability that each treatment is superior to placebo, $Pr(\exp(\theta_T) < 1)$, as well the mean and 95% credible intervals for each DRR.

Patient-specific multiplicative random effects in the slope, $\exp(\eta_i), i = 1, \dots, n$, represent the patient-specific proportional increase or decrease in the rate of progression. Covariate effects are modelled as $\alpha_c, c = 1, \dots, C$, and account for explained variability in the rate of NSAA progression due to subject-specific baseline covariates.

Random data source effects to account for the between-source variability in NSAA progression rates are modelled as $\delta_{s(i)}$, where the source of each patient is labelled $s(i)$ with 0 for this study and 1:S for the historical data sources. These source effects account for the variability in the rate of progression of NSAA between placebo and historical controls in the different data sources that are not explained by baseline covariates. For a patient randomized in this study, the source effect is assumed to be 1 ($\delta_0 = 0$).

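### If 3 mg/kg is stopped, 4.5 mg/kg to placebo allocation moves from 1:1 to 2:1; the NSAA model names no enrolment-stage term, so unexplained drift partly enters the 4.5 mg/kg contrast

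*Combined protocol and SAP*

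**What the plan says.** **Allocation.** Section 6.1.1 starts with "Patients will be randomized in a 1:1:2:2 ratio to placebo 3 mg/kg, placebo 4.5 mg/kg, WVE-210201 3 mg/kg, and WVE-210201 4.5 mg/kg". The analysis uses one placebo code ("with 0 for placebo, 1 for WVE-210201 3 mg/kg and 2 for WVE-210201 4.5 mg/kg"), so the two placebo groups form a single comparator and 4.5 mg/kg to placebo is 2:2, that is 1:1. Under Section 11.5.1, once 3 mg/kg is stopped, "all future patients will be randomized to WVE-210201 4.5 mg/kg or placebo at a 2:1 ratio".

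**NSAA analysis after a stop.** Section 11.3.2.2 says "the WVE-210201 treatment arms will not be pooled", and success then rests on the 4.5 mg/kg effect alone. Section 11.5.1 adds that boys moved from 3 to 4.5 mg/kg "will not be included in WVE-210201 4.5 mg/kg treatment effect estimation". NSAA is primary for EU/Japan and key secondary for the US/Other regions (Section 4.3.1).

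**NSAA model terms.** These are treatment, patient random effects, a covariate vector and a data-source effect. On covariates the text says "The model will include covariate effects to measure differences in the rates of progression based on patient-specific baseline covariates", without listing them. The source label is coded "with 0 for this study and 1:S for the historical data sources", with the effect for this study fixed at zero (δ₀ = 0), so both enrolment stages share one level.

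**Dystrophin model terms.** Section 11.3.2.1 says "The model will include fixed effects for mean change from baseline in dystrophin levels at each time point for placebo". Treatment effects and variances are also specific to time point. Biopsy week follows enrolment order (Section 4.1.2): patients 1–30 at Week 12, 31–70 at Week 22, the rest at Week 46.

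**Error control.** Section 11.3.3 sets a one-sided 2.5% family-wise rate and cites simulations. It mentions neither time drift nor the ratio change.

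**The concern.** When the allocation ratio changes during a trial and the analysis pools across the change, treatment becomes associated with enrolment period. Later boys would be over-represented on 4.5 mg/kg relative to placebo. If they decline more slowly for reasons unrelated to treatment, the drug gains credit; if they decline faster, it loses some. Possible routes are care practice, assessor training and region mix. The protocol itself makes region mix depend on time, because enrolment at Japanese sites is held after the first 12 patients until their data are reviewed (Section 4.1.2).

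The event that changes the ratio also makes the unpooled 4.5 mg/kg contrast the NSAA test, so the exposure falls on a confirmatory comparison.

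**Working it through.** **Inputs from the documents.** SD of NSAA change 4.5, difference 3.0, dropout 10%, N = 150 (Section 11.1); allocation as above. **Assumed:** the size of the unexplained drift, the enrolment number at the switch, and enrolment to the full 150.

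**The plan's own figure.** 150 × 0.9 = 135 completers. One dose against pooled placebo is 45 v 45, and a two-sample t-test gives 87.9% power (normal approximation 88.5%), matching the stated 88%. Both doses pooled, 90 v 45, would give 95.2%. The SD and dropout inputs are therefore used as the plan uses them.

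**Numbers randomized, switch after patient 70 (illustration)**

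| | Before | After | Total | Early share |
|---|---|---|---|---|
| Placebo | 70/3 = 23.3 | 80/3 = 26.7 | 50.0 | 46.7% |
| 4.5 mg/kg | 70/3 = 23.3 | 2 × 80/3 = 53.3 | 76.7 | 30.4% |

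**Bias without a stage term** = drift × (late share of 4.5 mg/kg − late share of placebo) = drift × (0.696 − 0.533) = 0.162 × drift, from unrounded shares.

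**Standard error** with 10% dropout (69 v 45): 4.5 × √(1/69 + 1/45) = 0.862.

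**One-sided error under the null** = 1 − Φ(1.960 − bias/SE):
- drift 0.5: bias 0.081, error 3.1%
- drift 1: bias 0.162, 1.960 − 0.188 = 1.772, error 3.8%
- drift 1 reversed: 1.960 + 0.188 = 2.148, error 1.6%

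A simulation of 100,000 trials of the same linear analogue gave 3.7% at a 1-point drift.

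**Other switch points, 1-point drift**

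| Switch after patient | Bias factor | Error |
|---|---|---|
| 30 | 0.089 | 3.2% |
| 50 | 0.133 | 3.6% |
| 70 | 0.162 | 3.8% |
| 90 | 0.171 | 3.9% |
| 120 | 0.133 | 3.5% |

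The factor peaks at 0.172 near patient 88.

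**With a stage term.** Completers are 21 v 21 before the switch and 48 v 24 after. The stage variances, in units of σ², are 1/21 + 1/21 = 0.0952 and 1/48 + 1/24 = 0.0625. The inverse-variance combination has SE = 4.5 × √(1/(10.5 + 16)) = 0.874, and 0.874/0.862 = 1.014. Simulated bias is about zero and error 2.5–2.6% for drifts of 0 to 3 points. Power for a 3-point difference goes from 93.6% to 92.9%.

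**Dystrophin.** Terms specific to time point compare each biopsy cohort only with itself. A switch exactly at patient 30 or 70 gives zero bias. A switch inside a cohort leaves a residue. For example, at patient 110 the factor within the Week 46 cohort is 0.167; with SD 3.0 and 10% dropout the SE is 0.791, and an assumed drift of 1 percentage point moves the per-look error from 0.83% to 1.45%. A switch inside a cohort is likely, because the interim results need Week 12 or Week 22 biopsies and no general enrolment pause is described.

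**The case against.** The strongest objection is that every magnitude depends on a drift for which the documents give no figure. One point is a third of the 3-point average yearly decline cited in Section 11.1. It would have to arise within one trial that has fixed eligibility and a stable-steroid requirement, and to survive covariate adjustment; region, for instance, could be a covariate. The sign is unknown, and averaging the two 1-point cases gives (3.8 + 1.6)/2 = 2.7%. This stands: the figures show sensitivity and do not predict inflation.

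Four stronger readings are tempting, and the documents do not support them:

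- **That the NSAA model certainly lacks a stage term.** No NSAA covariate is listed, and the SAP to which Section 11.5.1 refers for thresholds is not in the text reviewed. The text can only be said not to name one.
- **That dystrophin is biased in the same way.** Its model already separates the three enrolment cohorts.
- **That the trial's error rate is 3.8%.** That figure is conditional on 3 mg/kg being stopped, a switch at patient 70 and a favourable 1-point drift. The probability of the stop has not been estimated, and it dilutes any trial-wide effect.
- **That the calculation describes the planned analysis.** The plan uses a multiplicative Bayesian progression model with historical controls. The calculation is a linear analogue without borrowing, and the effect of borrowing on bias and precision is unknown.

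The structural point remains. A pre-planned adaptation changes the ratio, the single source level cannot absorb a difference between stages, and the text does not say that the analysis accounts for it.

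**Conclusion.** The point holds as a modest, conditional weakness of the NSAA analysis. If 3 mg/kg is stopped, between about 9% (switch at patient 30) and 17% (near patient 88) of any drift not explained by covariates passes into the 4.5 mg/kg contrast, in either direction. At a 1-point drift and a switch at patient 70, that is 0.16 points, or 0.19 standard errors, and about 5% of the 3-point design difference (0.162/3). For dystrophin, exposure is confined to a biopsy cohort that spans the switch.

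This rests on the assumed drift and switch point, on enrolment reaching 150, and on the covariate vector holding no stage or enrolment-time term. If the vector already holds one, the sponsor need only say so. The point is an inexpensive improvement and does not by itself undermine the design.

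**What to change.** Before the first dystrophin interim analysis, pre-specify the following for the case that 3 mg/kg is stopped:

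1. **NSAA model.** Include an indicator for randomization before or after the ratio change, applied to patients of this study only. State how historical controls, who have no enrolment stage, are coded, and which stage δ₀ = 0 anchors, since that decides which stage the borrowed information is tied to.
2. **Dystrophin model.** Add the same indicator only within a biopsy cohort that spans the change.
3. **Simulations.** Add drift scenarios, in both directions and over a range of switch points, to the type I error simulations cited in Section 11.3.3, with historical borrowing switched on.

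**Cost.** One extra parameter in the NSAA model. Before borrowing, the standard error rises about 1.4% (0.862 to 0.874) and power for a 3-point difference falls about 0.7 percentage points (93.6% to 92.9%) for a switch at patient 70. The cost with borrowing should come from the simulations. No change to trial conduct is needed.

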Summaries of the posterior distribution for the treatment difference in dystrophin compared to placebo at each time point for each arm will be provided including the probability that each treatment is superior to placebo at each time point, $\Pr(\theta_{T,j} > 0)$, as well as mean and 95% credible intervals.

The dystrophin analysis will be supplemented with dystrophin data from the ongoing Open-label extension study to the Phase 1 trial (WVE-DMDX51-002). These results will be available at the time of the first dystrophin interim analysis.

Missing dystrophin data can result from intercurrent events which include discontinuation of the study and non-evaluable biopsies. Previous pivotal studies in DMD, including exon skipping therapies, have had low study discontinuation rates (e.g. 0.6% and 2.7%) so it is anticipated that missing data resulting from study discontinuation will be limited (^{57,58}). With the selected estimand, missing dystrophin results due to study discontinuation will be handled using baseline imputation. Non-evaluable dystrophin will be addressed using imputation under the assumption of missing-at-random (MAR). The regression method for monotone missing data will be used for the multiple imputation with baseline dystrophin as a covariate and imputation stratified by treatment arm.

There will be two interim dystrophin efficacy analyses and a final dystrophin efficacy analysis. The dystrophin treatment effects will be declared significant at the interim or final analyses using a gatekeeping strategy where the WVE-210201 4.5 mg/kg arm is assessed first and, if significant, the WVE-210201 3 mg/kg arm is assessed. To account for the three possible analyses of the dystrophin treatment effects, a Bonferroni-level adjustment will be applied. A one-sided, significance threshold of $1 - (0.025/3) = 0.991667$ will be used for the Bayesian posterior probability of superiority of each dose compared to placebo. If successful for WVE-

210210 4.5 mg/kg, the same threshold will be used for WVE-210210 3 mg/kg. Specifically, success will be declared for WVE-210201 4.5 mg/kg if

1. $\Pr(\theta_{2,1} > 0) > 0.991667$ at the first dystrophin interim analysis,
2. $\Pr(\theta_{2,2} > 0) > 0.991667$ at the second dystrophin interim analysis, or
3. $\Pr(\theta_{2,3} > 0) > 0.991667$ at the final dystrophin analysis.

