With this plan, the 12-week WVE-210201 4.5 mg/kg treatment effect is assessed at the first dystrophin interim analysis, the 22-week WVE-210201 4.5 mg/kg treatment effect is tested at the second dystrophin interim analysis and the 46-week WVE-210201 4.5 mg/kg treatment effect is tested at the final dystrophin interim analysis. Similar comparisons will be made for the WVE-210201 3 mg/kg treatment effect if the 4.5 mg/kg treatment effect is significant.

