The residual errors for the individual observations, $\epsilon_{ij}, i = 1, \dots, n$ and $j = 0, \dots, 4$, are modelled as independent normal distributions with a treatment arm and source-specific standard deviation of $\sigma_{t(i),s(i)}$.

Missing NSAA data can result from intercurrent events which include discontinuation of the study and loss of ability to complete any NSAA activities. With the selected primary estimand, missing NSAA assessments or NSAA assessments collected after randomized therapy discontinuation will be imputed using a control-based imputation strategy for treated patients. Placebo patients will have missing observations imputed assuming MAR. The loss of the ability

to complete any NSAA activities will be recorded as 0 on the case report forms and used in the analysis.

The posterior probability that the DRR is less than 1 will be assessed to determine significance of the WVE-210201 NSAA treatment effect. Superiority on slowing the rate of decline on NSAA will be declared if the posterior probability that either 1) the pooled WVE-210201 treatment effect ($\theta_1 = \theta_2$; if the low dose has not been dropped) or 2) the WVE-210201 treatment effect θ_2 (if randomization to the WVE-210201 3 mg/kg has been stopped) is superior to placebo and slows the rate of NSAA progression is greater than 0.975:

$$\Pr(\exp(\theta_2) < 1) > 0.975.$$

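### After a 3 mg/kg stop, the plan would still test as the 3 mg/kg dystrophin effect an estimate built on patients switched to 4.5 mg/kg

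*Combined protocol and SAP*

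**What the plan says.** **The stop and the switch.** Section 11.5.1 allows randomization to 3 mg/kg to end on a dystrophin interim result. In that case "patients originally randomized to the 3 mg/kg treatment arm will be transitioned to the WVE-210201 4.5 mg/kg treatment arm", and later patients are randomized 2:1 to 4.5 mg/kg or placebo. On the stopping rule it adds only "The specific thresholds are included in the SAP".

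**Analysis of switched patients.** The same section has one sentence on this. It begins "For clinical endpoint analyses, including the NSAA, patients originally randomized to the WVE-210201 3 mg/kg arm who transition" and says that these patients do not contribute to the 4.5 mg/kg effect. Section 11.3.2.2 adapts the NSAA analysis as well. The doses are no longer pooled "if the randomization to the WVE-210201 3 mg/kg arm is stopped after an interim analysis", and the superiority claim rests on the 4.5 mg/kg parameter alone "if randomization to the WVE-210201 3 mg/kg has been stopped".

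**Dystrophin.** Section 11.3.2.1 names as its target "The treatment policy estimand, which assesses the effect of treatment initially assigned at baseline (regardless of adherence to the planned course of treatment"). Section 11.2.1 analyses patients as randomized, and Section 4.1.2 uses all biopsies in the primary efficacy analysis. The model gives each dose its own parameter at each biopsy time: θ1 for 3 mg/kg and θ2 for 4.5 mg/kg. Testing follows a "gatekeeping strategy where the WVE-210201 4.5 mg/kg arm is assessed first and, if significant, the WVE-210201 3 mg/kg arm is assessed", and "Similar comparisons will be made for the WVE-210201 3 mg/kg treatment effect if the 4.5 mg/kg treatment effect is significant". None of this mentions a stopped arm or a switch.

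**The concern.** Each patient has one post-baseline biopsy, at Week 12, 22 or 46 according to order of enrolment. If the 3 mg/kg arm is stopped at an interim, the 3 mg/kg patients in the next biopsy cohort will have been moved to 4.5 mg/kg before their biopsy. The stated rules still place them in θ1 and still test θ1 as the effect of 3 mg/kg.

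A positive test would then count as a confirmatory dystrophin success for 3 mg/kg. The muscle samples behind it would come from boys receiving 4.5 mg/kg, in an arm that was stopped because it looked weaker. Dystrophin is the primary endpoint for the United States, and the plan says that dystrophin results may support early registration, so the meaning of a dose-specific claim matters.

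**Working it through.** **Figures in the plan.** The threshold is 1 − 0.025/3 = 0.991667, as stated. For the stated dystrophin power, 150 × 0.9 = 135 evaluable patients, or 45 per dose and 45 pooled placebo. The noncentrality is 4 / (3 × √(1/45 + 1/45)) = 4 / 0.632 = 6.32, so power exceeds 99%, as stated.

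**Timing.** Let r be accrual per week and L the weeks from the last interim biopsy to the switch. Neither is in the plan.

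- *Second-interim stop.* Counted from enrolment of patient 70, the switch falls at week 22 + L. Patient 71 reaches the Week 46 biopsy at week 46 + 1/r. All Week 46 biopsies of still-treated 3 mg/kg patients are post-switch if L < 24.
- *First-interim stop.* Counted from patient 30, the switch falls at 12 + L and patient 31 reaches Week 22 at 22 + 1/r. The same holds for Week 22 biopsies if L < 10.
- *Biopsies at the look that triggers the stop* are all pre-switch.

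So at an affected look θ1 contains almost no data from patients on 3 mg/kg.

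**Size at Week 46 after a second-interim stop.** From Section 11.1: SD 3, 4 points at Week 46, 10% loss. Assumed: 3 mg/kg itself inert, effect linear in weeks on 4.5 mg/kg, L = 8, r = 1 or 2, immediate switch, and a one-sided t-test at 0.025/3 in place of the Bayesian model.

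The k-th patient after patient 70 has 46 − (30 − k/r) = 16 + k/r weeks on 4.5 mg/kg before biopsy.

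| | r = 1 | r = 2 |
|---|---|---|
| Enrolled at the stop, 70 + 30r | 100 | 130 |
| 3 mg/kg evaluable at Week 46 | 30/3 × 0.9 = 9 | 60/3 × 0.9 = 18 |
| Placebo evaluable, 80/3 × 0.9 | 24 | 24 |
| Mean weeks on 4.5 mg/kg | 16 + 15.5 = 31.5 | 16 + 15.25 = 31.25 |
| Mean effect, 4 × weeks/46 | 2.74 | 2.72 |
| Noncentrality | 2.74 / (3√(1/9 + 1/24)) = 2.34 | 2.72 / (3√(1/18 + 1/24)) = 2.91 |
| Both doses cross (simulated) | about 0.43 | about 0.64 |

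Repeat runs put the first figure at 0.42 to 0.43. The 4.5 mg/kg gate removes almost nothing, because that dose crosses in about 99% of runs. An inert dose with no switching crosses in 0.8%.

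**Sensitivity.** These ranges cover accrual of 1 to 3 per week and lags of 0 and 8 weeks.

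- *Week 46, full 4 points reached by Week 22 on 4.5 mg/kg:* both cross in 71% to 96%.
- *Week 46, flat effect of 1 or 2 points:* 2% to 3%, or 14% to 28%.
- *Week 22 look after a first-interim stop, linear effect:* 2% to 4%; with 4 points reached by Week 22, 11% to 37%.

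The linear Week 46 range over these six cases is 42% to 79%. The 79% needs zero lag. The case of 3 per week with an 8-week lag would have 70 + 3 × 30 = 160 due, above the 150 planned, so no randomization would remain to stop. Neither is used for the headline figure.

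Not modelled: the supplementary WVE-DMDX51-002 data (direction unknown), and baseline imputation and an early NSAA enrolment stop, both of which would lower the Week 46 figures.

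**The case against.** **The estimand is stated, and θ1 is valid under it.** Under treatment policy, θ1 is the effect of being assigned to 3 mg/kg, including a switch that the protocol directs. This stands. A reader might infer an inflated type I error, but the documents do not support that: assignment to that arm does have an effect when its patients then receive an active dose. What remains is that the tested quantity is named and claimed as the 3 mg/kg effect.

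**The NSAA rule is not a true precedent.** A reader might infer that the plan solved this problem for NSAA and forgot dystrophin. NSAA pools the doses and never has a separate 3 mg/kg test, so stopping that arm forces un-pooling. The dystrophin model already separates the doses. The NSAA rule is only a loose parallel.

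**Retesting is a reading.** Section 11.3.2.1 lists the three looks as alternatives. If 4.5 mg/kg passes at the look that triggers the stop, 3 mg/kg is tested there on pre-switch biopsies, and the text does not say in terms that testing is repeated. It does carry the 3 mg/kg comparison through all three looks with no exception for a stopped arm, so a later test is the natural reading.

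**The separate SAP may cover it.** It is not in the material reviewed, so this stands as a limit on confidence. Section 11.5.1 defers only thresholds to it, while the model, gate and success rule are all in Section 11.3.2.1.

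**Not every 3 mg/kg patient switches.** Sections 4.1.4 and 5.4.2 encourage patients who stop treatment to stay in the study. The timing statement therefore covers still-treated patients only.

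**An inert 3 mg/kg dose is unlikely on the sponsor's view.** Section 2.2 expects target engagement at both doses. The inert case shows how little the test would then say about the dose; it is not a forecast.

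**Conclusion.** The point holds, conditional on the stopping branch being taken and 4.5 mg/kg being significant at the later look. On the text supplied, a confirmatory 3 mg/kg dystrophin claim could rest almost wholly on patients receiving 4.5 mg/kg. The main exposure is the Week 46 look after a second-interim stop. A Week 46 3 mg/kg group after a first-interim stop needs more than 70 enrolled by then, which occurs in one of the six accrual and lag cases examined.

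The 43% to 64% is an illustration under assumed accrual, lag, effect shape and an inert 3 mg/kg dose. It is neither an error rate nor a prediction, and it falls to 2% to 3% with a flat 1-point effect.

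A reader might also infer that the 4.5 mg/kg result is contaminated. It is not: the as-randomized rule and the arm label keep switched patients out of θ2. This is a correction the plan should make, with medium confidence because the separate SAP was not available.

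**What to change.** Change analysis text only; dosing is not touched. In Sections 11.3.2.1 and 11.5.1, and in the SAP, state that after randomization to 3 mg/kg is stopped:

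1. no confirmatory 3 mg/kg dystrophin test is made at a look whose 3 mg/kg biopsies were taken after the switch;
2. any θ1 estimate that includes switched patients is descriptive and is labelled an effect of initial assignment, not of the 3 mg/kg dose.

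Optionally, confirm that switched patients stay out of θ2, which the as-randomized rule already implies. The test at the look that triggers the stop is unchanged.

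The cost is two or three sentences in each place, with no change to estimand, population, thresholds or sample size. The price is a later confirmatory claim for an arm already stopped as the weaker one. The wording should be fixed before any interim result is known, because added afterwards it would look data-driven.
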